#### 8.2.2 Exclusion Criteria

- 1. History of any comorbidity reviewed at screening that, in the opinion of the investigator, might confound the results of the study or pose an additional risk in administering LUM/IVA to the subject. For example, a history of cirrhosis with portal hypertension.
- 2. Any clinically significant laboratory abnormalities at screening that would interfere with the study assessments or pose an undue risk for the subject (as deemed by the investigator).
- 3. Any of the following abnormal laboratory values at screening:
  - Hemoglobin < 9.5 g/dL
  - Alanine aminotransferase (ALT), aspartate aminotransferase (AST), or total bilirubin >2 × upper limit of normal (ULN)
  - Chronic kidney disease of Stage 3 (estimated glomerular filtration rate [eGFR] <60 mL/min/1.73 m^2 calculated by the Bedside Schwartz equation) based on the normal range for eGFR in this age group (62 to 191)
- 4. An acute upper or lower respiratory infection, pulmonary exacerbation (PEx), or changes in therapy (including antibiotics) for pulmonary disease within 28 days before Day 1 (first dose of LUM/IVA).

- 5. A standard 12-lead ECG demonstrating QTc >450 msec at screening. If QTc exceeds 450 msec at the Screening Visit, the ECG should be repeated 2 more times during the Screening Period, and the average of the 3 QTc values should be used to determine the subject's eligibility.
- 6. History of solid organ or hematological transplantation.
- 7. Ongoing or prior participation in an investigational drug study (including studies investigating LUM and/or IVA) within 30 days of screening.
  - A washout period of 5 terminal half-lives of the previous investigational study drug, or 30 days, whichever is longer, must elapse before the Screening Visit.
  - The duration of the elapsed time may be longer if required by local regulations.

Note: Ongoing participation in a noninterventional study (including observational studies) is permitted.

[figure not shown]
- 8. Use of restricted medication or food within specified duration before the first dose of LUM/IVA as defined in Section 9.4.
- 9. An adequate slit-lamp examination could not be conducted at the Screening OE.

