## 12.3.5.2 Clinical Laboratory Assessments

For the laboratory measurements, the raw values and change from baseline of the continuous hematology and chemistry results will be summarized in SI units at each visit of the Current Study Period overall.

The number and percentage of subjects meeting the threshold analysis criterion during the TE Period of the Current Study Period will be summarized based on the 124 Safety Set overall. The threshold analysis criteria will be provided in the SAP.

In addition, a listing containing individual subject hematology and chemistry values outside the reference ranges will be provided. This listing will include data from scheduled and unscheduled visits.

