## 13.1.1.4 Adverse Event Severity

The investigator will determine and record the severity of all serious and nonserious AEs. The guidance available at the following website will be consulted: Toxicity Grading Scale for Healthy Adult and Adolescent Volunteers Enrolled in Preventive Vaccine Clinical Trials, September 2007, Center for Biologics Evaluation and Research,

https://www.fda.gov/downloads/BiologicsBloodVaccines/GuidanceComplianceRegulatoryInformation/Guidances/Vaccines/UCM091977.pdf (Accessed July 2018). When considering the severity of an AE in a pediatric subject, the investigator will consider that reference ranges for pediatric clinical laboratory parameters may differ from those in the vaccine scale. The severity of an AE described by a term that does not appear in this scale will be determined according to the definitions in Table 13-1.

**Table 13-1** Grading of AE Severity

Classification	Definition
Mild (Grade 1)	Mild level of discomfort and does not interfere with regular activities
Moderate (Grade 2)	Moderate level of discomfort and significantly interferes with regular activities
Severe (Grade 3)	Significant level of discomfort and prevents regular activities
Life-threatening	Any adverse drug event that places the subject, in the view of the investigator, at
(Grade 4)	immediate risk of death

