10.6.2 Clinical Laboratory

For laboratory measurements, raw values and change from baseline values for the continuous hematology and chemistry results will be summarized in SI units at each visit of the TE Period.

Laboratory tests done in the local laboratory may be used in data analyses if data from the central laboratory are not available.

For hematology and chemistry, the number and percentage of subjects with abnormally low (< lower limit of normal [LLN]) values and with abnormally high (> upper limit of normal [ULN]) values at each visit will be summarized.

The number and percentage of subjects meeting the threshold analysis criterion during the TE Period of the TE Period will be summarized for selected laboratory parameters based on the Safety Set. The threshold analysis criteria are provided in Appendix.

In addition, listings containing individual subject hematology and chemistry values outside of the normal reference ranges will be provided. These listings will include data from both scheduled and unscheduled visits.

LFT elevations meeting ALT or AST > 5xULN, or ALT > 3xULN and total bilirubin > 2xULN, or AST > 3xULN and total bilirubin > 2xULN at one visit during the TE period will also be listed.

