10.6.4 Vital Signs

For vital signs measurements, raw values and change from baseline values will be summarized at each visit of the TE Period for the following parameters: systolic and diastolic blood pressure (SBP/DBP) (mmHg), temperature (°C), pulse rate (beats per minute), respiratory rate (breaths per minute), weight (kg), length/height (cm), and BMI (kg/m²).

The number and percentage of subjects with at least one potentially abnormal SBP and/or DBP during the TE Period of the TE Period will be summarized separately based on the Safety Set using threshold criteria provided in Appendix. Potentially abnormal SBP and DBP by percentile (adjusted for sex, age, and length/height) will be provided, including:

- Number and percentage of subjects in categories: $\geq 90\%$ to < 95%; $\geq 95\%$ to < 99% + 5 mmHg; $\geq 99\% + 5$ mmHg, during the TE Period
- Number and percentage of subjects with SBP and DBP percentiles ≥95% at least once and at least twice during the TE Period
- Number and percentage of subjects with SBP and DBP percentiles ≥95% at each visit in the TE Period

The length/height adjustment will be based on length/height-for-age z-scores and their corresponding percentiles using the standard normal distribution (Appendix). The length/height percentiles will be further mapped per the following rules displayed in Table 9-1:

Table 9-1 Grouped Percentiles for Length/Height-for-Age Z-scores

Calculated Percentiles (%)	Grouped Percentiles (%)

0 – <7.5	5
7.5 – <17.5	10
17.5 – <37.5	25
37.5 – <62.5	50
62.5 – <82.5	75
82.5 – <92.5	90
92.5 – 100	95

The sex- and age-adjusted normal range for SBP and DBP for each grouped length/height percentile is based on the SBP/DBP table on the National Heart, Lung, and Blood Institute (NHLBI) website (http://www.nhlbi.nih.gov/health-pro/guidelines/current/hypertension-pediatric-jnc-4/blood-pressure-tables, accessed Oct 26, 2021).

Listings of subjects with potentially abnormal SBP and/or DBP will be provided.

The mean (+/- SD) value at each visit will be plotted separately for SBP and DBP.

Listings will be provided for vital signs parameters.

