Appendix D Criteria for Threshold Analysis

Table 11-4 Threshold Analysis Criteria for Laboratory Tests

Parameter	Categorical change	Comments			
Clinical Chemistry	Clinical Chemistry				
ALT	≤3xULN*(Not a categorical change) >3x - ≤ 5xULN >5x - ≤ 8xULN >3xULN >5xULN >5xULN >8xULN	FDA DILI Guidance Jul 2009.			
AST	≤3xULN*(Not a categorical change) >3x - ≤ 5xULN >5x - ≤ 8xULN >3xULN >5xULN >8xULN	FDA DILI Guidance Jul 2009.			
ALT or AST	ALT>3xULN or AST>3xULN	Vertex LFT working group 2014			
ALT or AST	ALT>5xULN or AST>5xULN				
ALT or AST	ALT>8xULN or AST>8xULN				
Alkaline Phosphatase	>1.5xULN	FDA DILI Guidance Jul 2009.			
Total Bilirubin	>1.5x - ≤2xULN >2xULN	FDA DILI Guidance Jul 2009.			
ALT and Total Bilirubin	ALT>3xULN and TBILI>2xULN	FDA DILI Guidance Jul 2009. To be counted within a same treatment phase, whatever the interval between measurements.			
AST and Total Bilirubin	AST>3xULN and TBILI>2xULN	FDA DILI Guidance Jul 2009. To be counted within a same treatment phase, whatever the interval between measurements.			
(ALT or AST) and Total Bilirubin	(ALT>3xULN or AST>3xULN) and TBILI>2×ULN	Vertex LFT working group 2014			
СРК	$>3x - \le 10xULN$ >10xULN	FDA criteria Feb 2005. Am J Cardiol April 2006.			
Creatinine	≥150 µmol/L (Adults) ≥30% change from baseline ≥100% change from baseline	Benichou C., 1994.			
Blood Urea Nitrogen	≥17 mmol/L				
Sodium	≤129 mmol/L ≥150 mmol/L				
Potassium	<3 mmol/L ≥5.5 mmol/L	FDA Feb 2005.			

Parameter	Categorical change	Comments
Glucose		
Hypoglycaemia Hyperglycaemia	≤3.9 mmol/L and <lln ≥11.1 mmol/L (unfasted); ≥7 mmol/L (fasted)</lln 	ADA May 2005. ADA Jan 2008.
Albumin	≤25 g/L	
Hematology		
WBC	<3.0 Giga/L (Non-Black); <2.0 Giga/L (Black) ≥16.0 Giga/L	Increase in WBC: not relevant. To be interpreted only if no differential count available.
Lymphocytes	>4.0 Giga/L	
Neutrophils	<1.5 Giga/L (Non-Black); <1.0 Giga/L (Black)	International Consensus meeting on drug- induced blood cytopenias, 1991. FDA criteria.
Monocytes	>0.7 Giga/L	
Basophils	>0.1 Giga/L	
Eosinophils	>0.5 Giga/L or >ULN (if ULN≥0.5 Giga/L)	Harrison- Principles of internal Medicine 17th Ed., 2008.
Hemoglobin	≤115 g/L (Male); ≤95 g/L (Female) ≥185 g/L (Male); ≥165 g/L (Female) Decrease from Baseline ≥20 g/L	Criteria based upon decrease from baseline are more relevant than based on absolute value. Other categories for decrease from baseline can be used (\geq 30 g/L, \geq 40 g/L, \geq 50 g/L).

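### The low-hemoglobin safety flag uses 115 g/L for boys and 95 g/L for girls with no stated age basis, so the pooled percentage reflects sex mix and starting level as well as any change on treatment

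*SAP*

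**What the plan says.** The hemoglobin row of SAP Table 11-4 has three criteria:

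- a low line, "≤115 g/L (Male); ≤95 g/L (Female");
- a high line, "≥185 g/L (Male); ≥165 g/L (Female");
- a decrease from baseline of at least 20 g/L, the same for both sexes.

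The row's comment reads: "Criteria based upon decrease from baseline are more relevant than based on absolute value". It gives no age range for the absolute limits and no reason for the difference between the sexes.

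SAP 10.6.2 turns each criterion into a count and a percentage of children, in these words: "threshold analysis criterion during the TE Period of the TE Period will be summarized for selected laboratory parameters based on the Safety Set". Protocol 12.3.5.2 has the same summary: "threshold analysis criterion during the TE Period of the Current Study Period will be summarized based on the 124 Safety Set overall". Neither states a split by sex or by whether the criterion was already met at baseline.

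On entry, Protocol 8.2.2 excludes LUM/IVA-naïve subjects with "Hemoglobin < 9.5 g/dL", for boys and girls alike. Protocol 8.1.2 sets no numeric hemoglobin limit for rollover subjects.

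Elsewhere the documents do allow for age. Protocol 13.1.1.4 reminds investigators that "reference ranges for pediatric clinical laboratory parameters may differ from those in the vaccine scale". SAP 10.6.4 says: "Potentially abnormal SBP and DBP by percentile (adjusted for sex, age, and length/height) will be provided".

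**The concern.** Clinical laboratory results are part of the primary safety endpoint. A percentage of subjects meeting a low-hemoglobin criterion during treatment will be read as information about treatment. Under this rule, two children with the same stable hemoglobin are classified differently according to sex, and a boy can be counted although nothing has changed since baseline. With about 50 subjects and no stated sex quota, the share of boys may well differ from one half, and the figure moves with it. A reader of the pooled table could not separate that from an effect of the drug.

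**Working it through.** The plan has no figure of its own to reproduce here. Steps 1 and 2 follow from the rule alone. Steps 3 to 6 are illustrations under assumptions.

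**Inputs from the documents.** Low limits 115 and 95 g/L (SAP Table 11-4). Naïve entry limit 9.5 g/dL (Protocol 8.2.2). Scheduled on-treatment hematology: nine draws for naïve subjects (Weeks 4, 12, 24, 36, 48, 60, 72, 84, 96; Protocol Table 3-2) and eight for rollover subjects (Weeks 12 to 84 and 96; Protocol Table 3-1).

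**Assumed inputs.** Mean m of 115, 120, 125 or 130 g/L; SD s of 8 or 10; within-child correlation 0.5 or 0.8; the same distribution in both sexes; no drug effect; constant true mean for each child.

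**Step 1, units.** 9.5 g/dL × 10 = 95 g/L. The girls' limit equals the naïve entry limit. The boys' limit lies 115 − 95 = 20 g/L above it.

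**Step 2, fall needed to be flagged** = max(0, starting value − limit).

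| Starting value (g/L) | Boy | Girl |
|---|---|---|
| 110 | 0 | 15 |
| 115 | 0 | 20 |
| 120 | 5 | 25 |
| 125 | 10 | 30 |

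**Step 3, one reading.** The share of eligible boys at or below 115 is [Φ((115−m)/s) − Φ((95−m)/s)] / [1 − Φ((95−m)/s)].

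- m = 130, s = 8: 0.030.
- m = 115, s = 8: (0.500 − 0.006)/(1 − 0.006) = 0.497.

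The share falls as the mean rises.

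**Step 4, repeated draws.** 400,000 simulated children in each of the 16 combinations (4 means × 2 SDs × 2 correlations). A child is flagged if any on-treatment value is at or below the limit.

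| Cohort | Boys flagged | Girls flagged | Flagged boys with no fall of ≥20 g/L |
|---|---|---|---|
| Naïve, 9 draws, baseline ≥95 | 9.7% to 90.0% | 0% to 11.4% | 80% to 100% |
| Rollover, 8 draws, no floor | 9.2% to 88.9% | 0% to 11.6% | 80% to 100% |

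At s = 8 and correlation 0.5, the naïve boys' rate falls from 0.90 at mean 115 to 0.16 at mean 130. That is the dependence on starting level.

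**Step 5, sex mix** (naïve, m = 120, s = 10). Overall percentage = p × boys' rate + (1 − p) × girls' rate, where p is the share of boys.

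- Correlation 0.8 (boys 0.567, girls 0.020): p = 0.4 gives 0.4 × 0.567 + 0.6 × 0.020 = 0.239; p = 0.6 gives 0.6 × 0.567 + 0.4 × 0.020 = 0.348.
- Correlation 0.5 (boys 0.745, girls 0.038): p = 0.4 gives 0.4 × 0.745 + 0.6 × 0.038 = 0.321; p = 0.6 gives 0.6 × 0.745 + 0.4 × 0.038 = 0.462.

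**Step 6, does a baseline condition alone cure it?** No. A separate run used means of 115 to 125 and between/within-child SDs of 6/5 or 8/6. Counting only boys with baseline above 115 lowered their flag rate from 35–87% to 29–75%, while girls were at 0–9%. The sex-specific limit itself has to be dealt with.

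**High line.** In the simulated scenarios no value reached 185 g/L and at most 0.2% of children reached 165 g/L. That gap matters for consistency only.

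**The case against.** The strongest reply is that the SAP largely covers this already. The same row has a sex-neutral decrease criterion and ranks such criteria above absolute ones. SAP 10.6.2 adds change from baseline, by-visit counts below the lower limit of normal, and listings of out-of-range values. There is no hypothesis test. All of that stands. It makes the point minor, but it does not make the pooled low-line percentage interpretable.

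Several stronger readings are tempting and not supported:

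- *The limits are adult values.* The hemoglobin row does not say so. An adult label appears only in the creatinine row. What can be said is that no age basis is stated.
- *A safety signal would be missed.* The displays named above do not use the 115/95 split.
- *Hemoglobin is the only such row.* Other rows also lack a stated age basis, and the white-cell and neutrophil limits differ between Black and non-Black subjects. Those rows were not assessed here.
- *The differing meaning of baseline in rollover and naïve subjects distorts this flag.* The absolute limits do not use baseline. That issue bears on the decrease criterion and on change from baseline.
- *95 g/L is the obvious common limit.* It is an entry limit for naïve subjects, not an analysis threshold chosen for this purpose. Applied to boys, it would cost sensitivity: at mean 120 and SD 10, a single limit of 95 g/L flags only 2% to 4% of naïve children.

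It is also fair to object that the magnitude is assumed and that a range of 10% to 90% says little about this trial's likely figure. That stands too. The simulation shows how the rule behaves, not what will be observed.

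**Conclusion.** The concern holds as a minor one, confined here to the hemoglobin row. By the rule alone, boys need 20 g/L less of a fall than girls from any starting value above 115 g/L, and no fall at all from 115 g/L or below. With no drug effect, the pooled percentage rises with the proportion of boys and falls as starting hemoglobin rises. That conclusion needs only that hemoglobin in the two sexes does not itself differ by anything like 20 g/L at this age.

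The sizes rest on the assumed mean, SD, correlation, identical sexes and constant true mean. The last is a simplification, since children age by 96 × 7 / 30.4375 = 22.1 months over the Treatment Period. Under those assumptions, about 10% to 90% of naïve boys and 0% to 11% of naïve girls are flagged. In the mid-range scenario, moving from 40% to 60% boys adds about 11 to 14 percentage points to the overall figure.

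**What to change.** In the hemoglobin row of SAP Table 11-4:

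1. Replace the sex-specific low and high lines with one analysis limit each for both sexes, preferably the laboratory's age-specific lower and upper reference limits. If the sex-specific lines are kept, state the reason and show the counts by sex.
2. Show the absolute low criterion as a shift from baseline category to lowest TE-Period value, following the pattern of SAP 10.6.6 for oximetry. Keep subjects who already met it at baseline in the table.
3. Keep the decrease of at least 20 g/L and present it first, as the row's comment supports.

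If the shift is shown by cohort, footnote that rollover baseline is taken after participation in the 24-week Study 122B Treatment Period, during which drug interruptions were allowed (Protocol 8.1.1).

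The cost is an edit to one appendix row and one extra display, with no new data or visits. Counts would no longer be comparable with any study that used the present limits. The reference-limit option partly overlaps the by-visit counts below the lower limit of normal, although it summarizes the whole TE Period rather than each visit. These are analysis limits only; eligibility and subject management are not affected.

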### 8.1.2 Exclusion Criteria

- 1. Prematurely discontinued LUM/IVA treatment in Study 122B.
- 2. History of any comorbidity or laboratory abnormality that, in the opinion of the investigator, might confound the results of the study or pose an additional risk in administering LUM/IVA to the subject (e.g., cirrhosis with portal hypertension).
- 3. History of drug intolerance or other serious reactions to LUM/IVA in Study 122B that would pose an additional risk to the subject in the opinion of investigator and which should be discussed with the Vertex medical monitor.
- 4. Subjects with a history of allergy or hypersensitivity to LUM/IVA.
- 5. Liver function test (LFT) abnormality meeting criteria for LUM/IVA treatment interruption at the completion of Study 122B, for which no convincing alternative etiology is identified.
- 6. QTc value at the completion of Study 122B that would pose an additional risk to the subject in the opinion of investigator, and should be discussed with the Vertex medical monitor (e.g., remained above the threshold value [>45 msec from baseline or >500 msec] on repeated measurement or was noted on 2 or more occasions with no identified alternative etiology for the increased QTc).
- 7. History of poor compliance with LUM/IVA and/or procedures in Study 122B as deemed by the investigator.
- 8. Participation in an investigational drug study (including studies investigating LUM and/or IVA) other than Study 122B. NOTE: Participation in a non-interventional study is permitted (including observational studies, registry studies, and studies requiring blood collections without administration of study drug).

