#### 12.3.5.3 Electrocardiogram

For the ECG measurements, the raw values and change from baseline values will be summarized at each visit of the Current Study Period overall, for the following standard digital ECG measurements: PR, QT, and QT corrected for HR (QTc) intervals (Fridericia's correction), QRS duration, and HR. In addition, the mean value (95% CI) at each visit will be plotted for QTcF.

The number and percentage of subjects meeting the threshold analysis criterion during the TE Period of the Current Study Period will be summarized based on the 124 Safety Set overall. The threshold analysis criteria will be provided in the SAP.

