10.6.3 Electrocardiogram

For ECG measurements, raw values and change from baseline values will be summarized at each visit of the TE Period for the following standard digital ECG measurements: RR (ms), PR (ms), QT (ms), QT corrected for HR (QTc) intervals (Fridericia's correction QTc (ms) = QT/RR^{1/3}), QRS duration (ms), and HR (bpm). In addition, the mean value (95% CI) at each visit will be plotted for QTc.

The number and percentage of subjects meeting the threshold analysis criterion during the TE Period of the TE Period will be summarized for selected ECG parameters based on the Safety Set. The threshold analysis criteria are provided in Appendix.

Listings will be provided for the ECG measurements.

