Platelets	<100 Giga/L ≥700 Giga/L	International Consensus meeting on drug- induced blood cytopenias, 1991.

Table 10-5 Threshold Analysis Criteria for ECGs

Parameter	Categorical change	Comments
HR	≤70 bpm	
	≥150 bpm	
PR		
	≥150 ms	
QRS	≥80 ms	
QTc	Absolute values (ms)	To be applied to any kind of QT correction formula.
	Prolonged: >450 ms (Male and Female)	

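### SAP Table 10-5 has no change-from-baseline category for QTc, so a rise of more than 45 ms that ends at or below 450 ms enters no count

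*SAP*

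**What the plan says.** Protocol 12.3.5.3 plans a count of subjects who meet ECG threshold criteria during the TE Period, and leaves their content to the SAP: "The threshold analysis criteria will be provided in the SAP". SAP 10.6.3 carries this out. Subjects who meet the appendix criteria "will be summarized for selected ECG parameters based on the Safety Set".

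The criteria are in SAP Appendix D, Table 10-5. The QTc row is headed "Absolute values (ms") and holds one line, "Prolonged: >450 ms (Male and Female"). No line for change from baseline and no line for values above 500 ms is printed.

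SAP 10.6.3 also covers QTc as a continuous variable: "raw values and change from baseline values will be summarized at each visit of the TE Period". It adds a plot of mean QTc by visit and listings of the ECG measurements.

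The protocol names a size of QTc change once, in exclusion criterion 6 for Rollover Subjects (Protocol 8.1.2). The criterion concerns a "QTc value at the completion of Study 122B that would pose an additional risk to the subject in the opinion of investigator", and gives as an example a value that "remained above the threshold value [>45 msec from baseline or >500 msec] on repeated measurement". For LUM/IVA-naïve Subjects the entry limit is absolute: "A standard 12-lead ECG demonstrating QTc >450 msec at screening" (Protocol 8.2.2).

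**The concern.** An absolute cut-off and a change cut-off answer different questions. The first asks whether a child's QTc is long, the second whether it has lengthened on treatment. Without a control arm, lengthening from the child's own baseline is the more direct signal, and the SAP gives no categorical count of it.

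The same appendix does use change from baseline elsewhere. Creatinine has categories for a rise of at least 30% and at least 100%, and hemoglobin has one for a fall of at least 20 g/L. The hemoglobin comment says that criteria based on the fall from baseline are more relevant than absolute ones. No reason is given for leaving such a category out for QTc.

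At stake is whether the report can say directly how many children had a marked QTc increase at any time on treatment.

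**Working it through.** The plan states no figure to reproduce. The check compares two rules.

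**Inputs**
- SAP flag (Table 10-5): post-baseline QTc > 450 ms.
- Change used for comparison: post-baseline minus baseline > 45 ms. This is the only QTc change value in the protocol (8.1.2, criterion 6, as an example).
- Upper value in the same example: > 500 ms.

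**When a rise above 45 ms is not counted**

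Both conditions must hold: post − baseline > 45 and post ≤ 450. Together they require baseline < 450 − 45 = 405 ms. In whole milliseconds the highest such baseline is 450 − 46 = 404 ms.

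| Baseline (ms) | Smallest rise that the SAP flags (451 − baseline) | Rises above 45 ms not counted |
|---|---|---|
| 360 | 91 | 46 to 90 |
| 380 | 71 | 46 to 70 |
| 400 | 51 | 46 to 50 |
| 404 | 47 | 46 only |
| 405 | 46 | none |

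**Values above 500 ms**

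Any value above 500 ms is also above 450 ms. It is counted, but cannot be told apart from 451–500 ms.

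**How many children could be affected**

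The documents give no baseline QTc distribution, so this is an assumption. If baseline is Normal with mean m and standard deviation s, the share below 405 ms is Φ((405 − m)/s).

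| Assumed mean (ms) | SD 15 | SD 20 |
|---|---|---|
| 380 | 95% | 89% |
| 390 | 84% | 77% |
| 400 | 63% | 60% |
| 410 | 37% | 40% |

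These are shares of children for whom an uncounted rise is arithmetically possible. They are not expected numbers of events.

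**Whether the other outputs fill the gap**
- *By-visit summaries.* SAP 10.1 includes the maximum, so the largest change at each visit is shown. It does not show how many children exceeded a given change, or whether the same child did so at several visits.
- *Record selection.* For safety parameters, SAP 10.1 uses only the record closest to the target day in each window. In Appendix A the Week 48 ECG window runs from day 254 to 505 (505 − 254 + 1 = 252 days), and the Week 96 window from day 506 to 680 (175 days). With a scheduled ECG on day 340, 3 days from the Week 48 target of 337, an unscheduled ECG on day 400, 63 days away, drops out of the by-visit summary. Protocol 11.4.5 provides for such repeat ECGs.
- *Listings.* They contain the values, but the reader must count. SAP 10.6.2 and 10.6.4 plan dedicated listings for liver test elevations and abnormal blood pressure. SAP 10.6.3 has none for QTc.
- *Maximum change.* SAP 10.1 already brings unscheduled visits into the derivation of maximum change from baseline, but no QTc category uses it.

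**The case against.** The strongest reply is that little is lost. This is a descriptive study of about 50 children with no hypothesis testing. Scheduled on-treatment ECGs are few: Weeks 24, 48 and 96, plus Weeks 4 and 12 for naïve children. Changes from baseline are summarized with their maximum, every ECG is listed, and Protocol 11.4.5 has investigators compare ECGs with baseline and record clinically significant abnormalities as AEs. The 450 ms category also matches the naïve entry limit. All of this stands, and it makes the point a minor one. It does not supply the missing count.

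A reader might infer that the SAP departs from a threshold fixed by the protocol. The documents do not support that. The 45 and 500 msec values are an example in an entry criterion for Rollover Subjects only. That criterion rests on the investigator's opinion and on a value that persists on repeat or recurs without another explanation. The protocol leaves the analysis criteria to the SAP, and a row for a single maximum rise would not reproduce the entry criterion.

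A reader might also infer that values above 500 ms are missed. They are not.

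A further objection concerns the baseline. Under SAP 10.1 it is the last value on or before the first Study 124 dose, which for Rollover Subjects comes after treatment in Study 122B. A rise above 45 ms would then mean different things in the two cohorts. This stands, and the new row has to deal with it.

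**Conclusion.** The point holds as a gap in the analysis categories. The only QTc category printed is an absolute value above 450 ms, so a rise of more than 45 ms that ends at or below 450 ms enters no TE-Period count. This is possible for any baseline below 405 ms. Values above 500 ms are counted but not shown separately.

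The size in this trial is unknown. The documents give neither a QTc distribution nor a rate of large rises, so they do not support saying that children will in fact be missed. The 37% to 95% range depends wholly on the assumed means and standard deviations.

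The conclusion assumes that Table 10-5 is complete as printed. Its PR row has a blank, so a lost QTc line cannot be fully excluded, although nothing in the text points to one. Importance is low. The change is still worth making, because ECGs belong to the primary endpoint and the data and derivation are already planned.

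**What to change.** Add one QTc row to Table 10-5: number and percentage of subjects whose maximum QTcF increase from baseline exceeds 45 ms at any time in the TE Period, scheduled and unscheduled ECGs included. State in a footnote that baseline is the last value on or before the first Study 124 dose. Note there that for Rollover Subjects this follows Study 122B treatment, or show the Rollover and naïve cohorts separately.

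Optionally, show values above 500 ms on a line of their own beneath the 450 ms line.

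If the sponsor prefers no change category, one sentence in the SAP should give the reason.

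The cost is one or two table rows and a footnote. No new data are needed, and SAP 10.1 already provides for deriving the maximum change from baseline. The downside is a slightly longer table.
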